database. Following completion of the program, pharmacy refill data will be collected for an additional 12 months to assess longer-term effects of the SEE Program.

Randomization: After baseline testing, participants will be given their randomization assignment. We will use block randomization stratified by site to allocate participants to the intervention or control groups. A randomization list using blocks of varying sizes (2, 4, and 6) will be produced in TATUM for each site. Block randomization maintains approximate group size balance during the trial. Varying the block size lowers the likelihood of knowing the group assignment of the next eligible participant. Randomized group status will be available to the research associate by email after baseline information and consent are entered into REDCap and eligibility is confirmed.

Retention strategies: Participants receive incentives: \$25 for each completed study visit and \$10/month for six months for using the electronic adherence monitor during the trial. The coaching program will be delivered free of charge. Participants randomized to the control arm will have the opportunity to schedule a free coaching session after completing all follow-up assessments. Participants will be given \$15 to defray travel costs for each study visit. If a participant has no other means of transportation and lives within 10 miles of the clinic, transportation will be arranged instead of the travel reimbursement.

The research associates will make multiple attempts to re-schedule missed appointments within a one-month window. We will also employ a combination of retention strategies, including pre-appointment reminder calling, phone follow-up of missed appointments, updating of contact information at each visit, and distribution of materials with study phone numbers. Participants will receive a birthday card mailed to their address from the study team.

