### **Intervention and Control Conditions**

The SEE Program is a six-month personalized glaucoma coaching program. The glaucoma coach goes over tailored education from a web-based application and uses MI-based counseling to help glaucoma patients identify their barriers to optimal medication adherence and explore potential solutions. Participants attend three in-person coaching sessions. The coach also gives between-session support through four phone calls, with two phone calls between the first and second session and one phone call after each following session. Participants can elect to receive any or none of the following alarms/reminders: an audible alarm, a visual alarm, a text message one hour after a dose of medication is missed or a text message one hour after a dose of medication is missed. (**Figure 1**) The control group received enhanced standard care, receiving three mailings of glaucoma educational materials from leading eye care institutions in parallel to the three in-person coaching sessions. Glaucoma medication adherence will be monitored electronically for all participants between the baseline visit and the exit visit six months later.

[figure not shown]

Figure 1. Schedule of SEE Trial visits for Intervention and Control arms; Primary Outcome Assessment at 6 months

**Intervention:** During the first in-person coaching session, the glaucoma coach uses a web-based application to generate tailored glaucoma educational materials and teach eye drop instillation. The education is tailored on the following variables: name, gender, race/ethnicity, type of glaucoma, glaucoma test results (visual field tests and optic nerve photographs), previous laser or incisional glaucoma surgeries, recommended glaucoma medications, physician's name, cell phone and internet usage, social support, and barriers to adherence. The application also generates MI-based counseling prompts to guide the conversation between the coach and

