Patients will receive approximately 160 minutes of counseling (120 minutes in-person and four 10-minute telephone calls). This is within the range of counseling time ( $106 \pm 92.4$  minutes) that achieved significant behavior change in a meta-analysis. The glaucoma coaches update the participants' ophthalmologist on their adherence and action plan. Participants can call their coach if questions arise.

**Control condition, enhanced standard care:** The purpose of the trial is to measure whether the SEE glaucoma counseling program improves glaucoma medication adherence compared to current practice. Therefore, we chose to use enhanced standard physician care as the comparator to control for the attention effect given by additional education without greatly changing the comparator group from what would currently be delivered in clinic. The enhanced standard care group will receive non-tailored educational content by mail from current gold standard providers (American Academy of Ophthalmology, National Eye Institute and Glaucoma Research Foundation) in three doses parallel to the three in-person coaching sessions.

**Sub-Study:** At the end of the six-month trial, we will ask all intervention participants if they would like to enroll in the twelve-month sub-study for continued medication adherence using their same adherence monitors. Participants will be reconsented for the sub-study and will receive incentives of \$10/month by gift card or check in the mail for medication monitoring along with a retention letter. No reminders will be set on the medication monitors during this twelve-month period and participants will have no contact with the study team except for a call as a reminder to charge monitors if needed.

Participants in the sub-study will be scheduled for a final exit visit at the end of this twelve-month period. During the final exit visit, participants will complete the same surveys as in the six-month exit visit, less the Satisfaction with SEE survey and have their IOP's measured by the study team. Participants will receive a \$25 incentive for the visit and \$15 to offset transportation costs.

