### **Statistical Analysis Plan**

We will perform intent-to-treat analysis of all randomized participants to evaluate our primary, secondary and exploratory outcomes. We will compare the primary outcome variable, mean adherence, between the two groups using ANOVA, blocking on clinic. We will also analyze the proportion of subjects achieving  $\geq 80\%$  adherence between the treatment group and control group, with the Cochran-Mantel-Haenszel Test for equality of proportions. We will use Student's t-test on post-trial, 12-month medication possession ratios to assess longer-term effects of the SEE Program compared to enhanced standard care.

Additionally, we will use pre-trial medication possession ratios in ANCOVA to investigate whether treatment effectiveness is steady across different levels of pre-trial adherence. We will conduct a sensitivity analysis to test mean adherence between the two groups with ANOVA, blocking on clinic. To investigate trends in adherence over time, we will calculate adherence monthly. Spaghetti plots will visualize trends within the treatment and control groups (linear, step, decaying effect, etc.). Linear regression will test for trends of adherence over time by treatment group.

For the secondary outcome of glaucoma related distress (GRD), we will score the scale according to the measure's documentation at the baseline and exit visits and calculate change. Descriptive statistics and plots will be generated to understand the distribution of scores and change, overall and stratified by treatment group and clinic. The exit GRD score will be regressed on treatment group, adjusted for baseline GRD and clinic.

For the exploratory IOP outcome, exit IOPs will be analyzed using measures from both eyes. The distribution of IOP and IOP change will be assessed with descriptive statistics and plots. The effect of treatment on IOP will be assessed with a linear mixed regression model, adjusting for baseline IOP and clinic, and controlling for the correlation between eyes of a subject with a random subject effect.

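### The 12-month refill comparison does not isolate the lasting effect of SEE: only SEE participants are offered paid monitoring in that window, and control coaching can fall inside it

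*Combined protocol and SAP*

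**What the plan says.** Four parts of the combined protocol and SAP bear on this point.

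- **Statistical Analysis Plan.** A Student's t-test will be run on post-trial "12-month medication possession ratios to assess longer-term effects of the SEE Program compared to enhanced standard care".
- **Participant Assessments.** This paragraph sets the window. Once the program is complete, "pharmacy refill data will be collected for an additional 12 months to assess longer-term effects of the SEE Program".
- **Sub-Study (under Intervention and Control Conditions).** When the six-month trial ends, "we will ask all intervention participants if they would like to enroll in the twelve-month sub-study for continued medication adherence". Participants consent again and keep the same monitors. They receive $10 a month "by gift card or check in the mail for medication monitoring along with a retention letter", and a final visit at the end of the 12 months pays $25 plus $15 for travel. No reminders are set, and "participants will have no contact with the study team except for a call as a reminder to charge monitors if needed". No matching offer to controls is described.
- **Retention strategies.** "Participants randomized to the control arm will have the opportunity to schedule a free coaching session after completing all follow-up assessments". No date is attached.

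During the trial itself the arms are balanced on monitoring and its payment. Intervention and Control Conditions states that "Glaucoma medication adherence will be monitored electronically for all participants between the baseline visit and the exit visit six months later", and the $10 a month for using the monitor is listed under Retention strategies for participants generally.

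**The concern.** The test is meant to show whether the benefit of a six-month program lasts. That reading requires the arms to differ after month six only in having received SEE or enhanced standard care. The plan adds a second difference that is certain, since one arm alone is offered paid monitoring. It adds a third that is possible, since the other arm may be coached. Both act on the behaviour that the possession ratio is meant to capture. The analysis plan neither separates them nor says that the contrast includes them.

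The refill comparison is the only planned comparison of the arms beyond month six, because the sub-study has no control group. If the result is reported as the longer-term effect of SEE, some of a positive difference could come from continued paid monitoring. Some of a null result could come from controls who were coached.

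**Working it through.** **Step 1. Set the periods side by side.**

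| | Months 0–6 | Months 6–18 (refill window) |
|---|---|---|
| SEE arm | Coaching; electronic monitor; $10 a month | Offer of monitor, $10 a month, retention letter, charging calls if needed, paid visit at the end |
| Control arm | Mailed education; electronic monitor; $10 a month | No monitoring offer; free coaching session, date not stated |

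The sub-study starts when the refill window starts and lasts the same 12 months. It is not part of SEE, which the protocol defines as a six-month program, and it needs fresh consent. This half of the point needs no inference.

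**Step 2. Place the control coaching session.** The session comes after follow-up assessments are complete, and two readings are open.

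- Participants complete visits and surveys, and a control has none after the month-six exit visit. On this reading, which is the more natural one, the session can be booked inside the refill window.
- The refill collection is itself described under Participant Assessments, so the phrase could include it. On this reading the session falls after month 18.

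The text does not decide between them.

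**Step 3. Look for a safeguard.** The Statistical Analysis Plan has no adjustment, no sensitivity analysis and no statement of the contrast that deals with either offer. Intent-to-treat is stated for the primary, secondary and exploratory outcomes, and the possession ratio is not one of the outcomes named under those labels. Even if applied, it would give a valid comparison of the arms as offered, which is a different contrast from the one named.

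**Step 4. Reproduce the nearest planning figure.** The documents give no standard deviation (SD), target or power for the 12-month ratio. The nearest figure, under Sample Size Aim 1, is 97 per arm for 80% power at 8 points with SD 20, for six-month electronic adherence.

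- n per arm = 2 × (1.960 + 0.842)² × 20² / 8² = 98.1, rounded up to 99, within 3% of 97.
- Standard error at 97 per arm = 20 × √(2/97) = 2.87. Power = Φ(8/2.87 − 1.96) = 79.6%.

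The stated figure is reproduced.

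**Step 5. Illustrate how the shift behaves.** Every input here is an assumption, including SD 20 for the refill ratio and 97 per arm with refill data.

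Shift in the mean difference = u × m − c × k, where u is the share of the SEE arm in the sub-study, m the refill-ratio points gained from monitoring, c the share of controls coached in the window, and k the points gained from coaching.

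| Scenario | Shift (points) | Chance of a significant result |
|---|---|---|
| No lasting SEE effect; u = 0.5, m = 2 | +1.0 | 6.4% (nominal 5%) |
| No lasting SEE effect; u = 0.5, m = 5 | +2.5 | 14.0% |
| No lasting SEE effect; u = 0.75, m = 10 | +7.5 | 74.3% |
| True lasting 8 points; c = 0.25, k = 5 | −1.25 | 65.2% (79.6% without coaching) |
| True lasting 8 points; c = 0.5, k = 5 | −2.5 | 48.2% |
| Both offers act; u = 0.5, m = 5, c = 0.5, k = 5 | 0 | as if neither acted |

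The shift runs from negligible to large, and it can take either sign or cancel. The documents contain nothing that narrows it.

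**The case against.** The strongest reply is that the sub-study is a weak co-intervention. It is voluntary, sets no reminders and limits contact to charging calls. Its payment is for monitoring and is not tied to adherence or refills. Its paid visit comes at the end of the window, and the endpoint is pharmacy refills, not monitor data. All of this stands. It argues for a small shift, such as the first row of the illustration, but it does not make the two arms' offers the same.

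A second reply is that coaching inside the window is not established. This also stands. A reader might infer that controls will be coached at about month six, but the protocol gives no date and the later reading is open. What can be said is that the wording permits it.

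A third reply is that the 8-point planning difference is no yardstick here. It belongs to on-time doses recorded electronically, while this endpoint is a refill ratio with no stated SD. That is correct. The illustrated percentages show how the comparison could behave and are not estimates for this trial.

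Finally, the possession ratio has one sentence in the analysis plan and is not a named primary, secondary or exploratory outcome. That limits the importance of the point. The sentence still commits the trial to a reading that the design does not deliver.

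**Conclusion.** The point holds in a limited form. The 12-month t-test compares SEE plus the offer of paid monitoring with enhanced standard care, possibly plus a coaching session. It does not isolate the longer-term effect of SEE against enhanced standard care. The sub-study half rests on explicit text. The coaching half rests on an undated phrase.

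The size and net direction of the shift cannot be determined from the documents. A reader might infer that the comparison is biased toward SEE, or that no result from it could be used. Neither is supported. The two offers would be expected to act in opposite directions with unknown uptake and effect. The randomised comparison of the arms as offered remains valid once it is described as such, and control coaching, if it took place, would tend to make a positive result conservative. The six-month primary outcome is untouched, because both offers come after it is measured.

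**What to change.** 1. **Retention strategies:** state that the control coaching session is offered only after the 12-month refill window has closed. This is one sentence. Its cost is that controls wait longer for the session.
2. **Statistical Analysis Plan:** state that the 12-month comparison includes the sub-study offer made to the SEE arm only, and make no claim about the lasting effect of SEE alone. This costs nothing beyond a narrower conclusion.
3. **Record and report by arm:** sub-study enrolment, and the date of any control coaching session. This is a small addition to data collection.

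Opening the sub-study to controls on the same terms would remove that imbalance, but it is optional because it needs extra resources. Participant payments would be at most 115 × (12 × $10 + $25 + $15) = 115 × $160 = $18,400. Staff time and equipment come on top, and the documents do not say whether controls keep their monitors. It would also move the control arm further from current practice, which the protocol gives as the comparator.

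Cutting control refill data at the coaching date is not advised, even as a sensitivity analysis. It would truncate one arm at a self-selected event after randomisation, which gives unequal windows and adds selection bias.

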**Participant Assessments:** After eligibility has been confirmed and informed consent has been obtained, prior to randomization, a research associate will measure participants’ intraocular pressure (IOP), record socio-demographic characteristics, administer a baseline survey including measures of glaucoma-related distress, glaucoma knowledge, perceived competence, motivation, self-efficacy, and autonomy support from their eye care team. IOP measurements will be taken at all in-person study visits. Surveys will be administered by study staff on a tablet with the ability to enlarge the font or have the survey read out loud. Eye drop instillation will be video-recorded. Additionally, we will use commercially available inertial measurement unit sensors (Xsens-dot, Movella, Netherlands) to assess the kinematics of all eye drop instillations. The sensor will be attached to the bottom of the artificial tear by a custom made silicone sleeve and will not interfere with the dispensing of the artificial tears. Snellen visual acuity will be recorded on all participants. Humphrey visual field testing (SITA Fast, 24-2) will be performed on participants who have not had a reliable visual field (SITA, 24-2) within the last year. Participants will be randomized to the SEE Program (experimental) or enhanced standard care by the physician with additional written education materials (control). Medication adherence will be monitored electronically for all participants from baseline through the end of the 6-month program period. A baseline measure of medication adherence will be obtained by an objective method (medication possession ratios assessed from pharmacy refill data for six months prior to study participation) and subjective method (survey). After six-months, a research associate will video-record eye drop instillation, administer a survey with the same behavioral and psychosocial measures and a quantitative program evaluation, and then a masked research associate will measure IOP and conduct a 15-30 minute semi-structured interview with participants in the SEE Program arm to assess their experience with the program. Additionally, we will call participants that do or did not return for the exit visit to ask if they will complete the exit surveys over the phone. All data will be entered into the REDCap

---

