## OUTCOMES

**Primary Outcome:** Six-Month Medication Schedule Adherence. Medication adherence will be measured objectively using electronic monitors with a bottle-in-bottle technique where all glaucoma medications are placed inside electronic pill bottles. When the bottle cap is removed, the time and date stamp is sent to our database. An adherent event is defined as using an eye drop medication within a specified time window of a dose on the previous day. For example, for an eye drop medication dosed once per day, an adherent event is defined as taking the medication within  $24 \pm 4$  hours of the previous day's dose. We include this time window because the biological efficacy of eye drop medications decline when not taken on time. We will compare the current day's doses to the previous day's corresponding doses, ensuring that opening a bottle multiple times prior to a clinic visit does not inflate the adherence metric. Adherence will be calculated as the proportion of doses taken on time divided by total doses prescribed over the six-month study period. For participants on more than one medication,

adherence will be first measured at the medication level and then aggregated to the person level by dividing the total number of doses of all medication(s) taken on time by the total number of doses prescribed. Our primary outcome is the mean adherence in the control and intervention groups. We will also assess the proportion of patients who are  $\geq 80\%$  adherent.

**Secondary Outcome:** Glaucoma-related Distress. Glaucoma-related distress, or the emotional distress participants experience related to having glaucoma, will be measured using the Diabetes Distress Scale adapted for glaucoma (Cronbach's  $\alpha = 0.93$ ). The Diabetes Distress Scale consists of 17 items with four subscales that measure emotional burden (5 items), physician-related distress (4 items), regimen-related distress (5 items), and diabetes-related interpersonal distress (3 items). In our pilot validation study of three items from the regimen-related distress and emotional burden subscales in a glaucoma population, we found a significant association of increased glaucoma-related distress with poor electronically monitored glaucoma medication adherence (adjusted  $\beta = -2.47$ , standard error (SE) = 0.61,  $p=0.0001$ ).

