### **Sample Size Aim 1: Compare the efficacy of the SEE Program with enhanced standard care in improving glaucoma medication adherence.**

We conducted brief interviews with 25 glaucoma specialists from throughout the US to gauge expert opinion regarding clinically important effect size. Their average recommendation for difference of group proportions of good adherence was 18.5 percentage points (95% CI 15.6-

21.5). Their average recommendation for difference of group mean adherence was 17.7 percentage points (95% CI 14.6-20.8). Additionally, mean medication adherence increased by 20 percentage points in our SEE Program pilot study from 65.7% ( $\pm 10.3$ ) at baseline to 85.7% ( $\pm 11.8$ ) after the program. With 97 participants in each group, a t-test has 80% power to detect a difference of 8 percentage points in mean adherence between the two groups, if the within group standard deviation (SD) is 20 ( $0.40 \times 20 = 8$ ). In our preliminary data the SD was 18, but we anticipate and plan for a possibly more diverse study group (calculated using R 'pwr' package). Our glaucoma specialists were divided on the importance of clinically important effect size, so we plan to be adequately powered for both continuous and binary adherence measures. Their average recommendation for difference of group proportions of good adherence was 18.5 percentage points (95% CI 15.6-21.5). The proposed sample size (n=97 per group) provides 80% power (at two-sided  $\alpha=0.05$ ) for Pearson's Chi Square Test of Independence to find a difference of 20 percentage points for the proportion of patients attaining good ( $\geq 80\%$ ) adherence between the intervention and control groups.

For our secondary outcome, with this sample size, we can detect a 1.1-point difference in mean change in Glaucoma Related Distress (scale 6-18) between trial arms if the SD is 2.8, as it was in our preliminary data. For this sample size in our exploratory outcome, we can detect a 1.9 mmHg difference in mean change in IOP between trial arms if the SD is 4.6 mmHg, as it was in our preliminary data. Although we will make concerted efforts to maximize retention, we will prepare for up to a 20% loss to follow-up as was experienced in our preliminary study and will enroll 115 participants in each arm for a total of 230 participants.

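### The sensitivity analysis of mean adherence repeats the primary analysis and cannot support it; a comparison adjusted for the pre-trial possession ratio should take its place

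*Combined protocol and SAP*

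**What the plan says.** The Statistical Analysis Plan opens by fixing one population for every outcome: "We will perform intent-to-treat analysis of all randomized participants to evaluate our primary, secondary and exploratory outcomes". The primary analysis follows: "We will compare the primary outcome variable, mean adherence, between the two groups using ANOVA, blocking on clinic". One paragraph later comes the sensitivity analysis: "We will conduct a sensitivity analysis to test mean adherence between the two groups with ANOVA, blocking on clinic".

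The sentence just before the sensitivity analysis brings in pre-trial refill data for a different purpose: "we will use pre-trial medication possession ratios in ANCOVA to investigate whether treatment effectiveness is steady" across levels of pre-trial adherence. Participant Assessments describes that variable, as a baseline measure of adherence, as "medication possession ratios assessed from pharmacy refill data for six months prior to study participation". Electronic monitoring starts only at baseline ("Medication adherence will be monitored electronically for all participants from baseline through the end of the 6-month program period"), so no pre-trial value of the outcome itself exists.

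Under Outcomes, the endpoint is defined as follows: "Adherence will be calculated as the proportion of doses taken on time divided by total doses prescribed over the six-month study period". The Aim 1 sample size section adds "we will prepare for up to a 20% loss to follow-up".

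**The concern.** A sensitivity analysis is informative only if it changes something: the population, the outcome definition, the handling of missing data, or the model. Here nothing is changed. This is the only analysis that the plan labels as a sensitivity analysis for mean adherence. If it is run as written, a report could say that the primary result was confirmed in a sensitivity analysis when the same model had been fitted twice to the same data.

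The plan also gives no covariate-adjusted estimate of the overall arm difference in adherence, although its models for distress and intraocular pressure do adjust for the baseline value. The variable needed for such an estimate is already due to be collected.

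**Working it through.** **1. The two specifications side by side (Statistical Analysis Plan)**

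| Element | Primary | Sensitivity |
|---|---|---|
| Outcome | mean adherence | mean adherence |
| Groups | two arms | two arms |
| Model | ANOVA | ANOVA |
| Blocking factor | clinic | clinic |
| Population | all randomized | all randomized (opening sentence) |
| Other adherence definition, covariate or missing-data rule | none named | none named |

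The same model on the same data gives the same estimate, standard error and p-value. The difference between the two analyses is zero by construction.

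**2. Do other planned analyses fill the gap?**

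- The Cochran-Mantel-Haenszel test uses a different, binary endpoint (at least 80% adherence).
- The ANCOVA with the possession ratio asks whether the effect varies with pre-trial adherence. No adjusted overall effect is specified from it.
- The regression of continuous adherence under Specific Aim 2 is adjusted for confounders that are not listed, and it serves the test of the income moderator.

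None of these is named as the sensitivity analysis for mean adherence, and none is specified to report an adjusted overall arm difference.

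**3. The plan's own power figure**

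Inputs from the Aim 1 sample size section: 97 per group, difference 8 points, SD 20. Two-sided alpha of 0.05 is stated there for the binary endpoint and assumed here for the mean as well.

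- SE = 20 × √(2/97) = 2.87; noncentrality = 8/2.87 = 2.79; noncentral-t power = 79.2%. The stated 80% is reproduced.
- With 115 per arm and the full 20% loss, 115 × 0.80 = 92 remain. SE = 20 × √(2/92) = 2.95; power = 77.0%.

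**4. What the replacement ANCOVA would do**

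Let r be the within-arm correlation of the possession ratio with monitored adherence. The documents do not give r, so a range is assumed. With no missing ratios, residual SD = 20 × √(1 − r²). For example, r = 0.3 gives SD 19.08, SE 2.81 and power 80.8% at 92 per arm.

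A simulation allowed for missing ratios: 160,000 trials per value of r, two equal sites with site in both models, normal outcome and ratio, and 15% of ratios missing at random (assumed). Missing ratios were handled by site-mean imputation plus a missing indicator. Difference 8, SD 20, 92 per arm:

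| r | Power, no missing ratios | Simulated power, ANOVA to ANCOVA | Change (points) | ANCOVA interval wider | Mean half-width (ANOVA 5.81) | Median shift of estimate (points) |
|---|---|---|---|---|---|---|
| 0 | 77.0% | 77.0% to 76.6% | -0.4 | 82% of trials | 5.84 | 0.15 |
| 0.1 | 77.4% | 77.0% to 76.9% | -0.1 | 62% | 5.82 | 0.21 |
| 0.2 | 78.6% | 77.1% to 78.0% | +0.9 | 23% | 5.74 | 0.36 |
| 0.3 | 80.8% | 76.9% to 79.7% | +2.8 | 3% | 5.61 | 0.54 |
| 0.5 | 87.6% | 77.0% to 85.7% | +8.7 | 0% | 5.18 | 0.91 |

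If all 115 per arm contribute, unadjusted power is already 85.6%, and the changes are -0.3, 0.0, +0.9, +2.4 and +6.8 points.

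**5. What the ANCOVA does not reach**

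Suppose 20% of each arm had no monitor data (assumed). Suppose too that unobserved intervention participants were 10 points less adherent than observed ones, with no such gap in control. The all-randomized difference would then move by 0.20 × 10 = 2 points. Adjustment for the possession ratio is not a test of that.

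**The case against.** The strongest case on the other side has four parts.

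- **It is a slip of wording.** The sentence follows directly on the ANCOVA and may have been meant as its unadjusted companion, or some variation may have dropped out of the text. That is possible, but the unadjusted ANOVA is already the primary analysis, so the companion reading still repeats it. The documents do not say what other variation was meant.
- **Covariates are already used.** With a centred ratio, even the model for steadiness of effect would yield an adjusted arm effect, and Specific Aim 2 has a covariate-adjusted adherence model. This stands in part: the plan is not without other views of adherence. Neither model, however, is specified to report an adjusted overall difference.
- **The gain is speculative.** This stands. It rests on an unknown r and an assumed rate of missing ratios, it is nil or slightly negative at r of 0.1 or less, and at the specialists' 17.7-point difference unadjusted power already exceeds 99.9%. Precision is therefore not the main reason for the change.
- **The remedy is narrow.** This also stands. Under randomization, ANOVA and main-effect ANCOVA estimate the same mean difference, so the replacement checks chance imbalance and precision. It does not check missing outcome data.

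A reader might infer that the primary analysis is biased or must become an ANCOVA because it leaves out the possession ratio. The documents do not support that. The arms are randomized, the ANOVA is valid without the covariate, and the ratio is a refill-based proxy whose correlation with the outcome is not reported.

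**Conclusion.** The point holds in a limited form. The planned sensitivity analysis duplicates the primary analysis and cannot lend it any support. This follows from the text alone and needs no numerical assumption.

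The case for the ANCOVA as the replacement is more modest. It gives a real check against chance imbalance in pre-trial adherence. In the simulation it moved the estimate by a median of 0.15 to 0.91 points for r from 0 to 0.5. Under the assumed 15% missing ratios it improves precision on average only from r of roughly 0.2 upwards. Those figures rest on the assumed r and missing rate, on SD 20, and on 92 per arm, which is the worst case of the loss the plan allows for.

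It would go too far to read this as a flaw in the primary result, or to read the ANCOVA as settling robustness to lost monitor data. Making the ANCOVA primary is optional and does not follow from this point.

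**What to change.** Before outcomes are seen by arm, amend the Statistical Analysis Plan as follows.

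1. Leave the primary ANOVA unchanged.
2. Replace the sensitivity sentence with a main-effect ANCOVA of mean adherence on arm, the same clinic blocking factor as the primary, and the six-month pre-trial possession ratio. Handle missing ratios by site-mean imputation plus a missing indicator. Report the adjusted arm difference with a 95% CI. Randomization is stratified by site while the analysis blocks on clinic, and the documents do not say whether these are the same. The blocking factor should therefore be identical in both models, so that only the covariate changes.
3. Keep the question of steady effect across pre-trial adherence as a separate analysis.
4. If the sensitivity analysis was meant to vary the handling of unmonitored days or the on-time window, name the rule that is varied. The endpoint divides by all prescribed doses and does not say how unmonitored days count.

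The cost is SAP wording, since collection of the ratio is already planned. The downside falls on the sensitivity analysis only. If the ratio is uninformative and 15% of values are missing, its interval is slightly wider in about 82% of trials (mean half-width 5.84 against 5.81), and its power is about 0.4 points lower at 92 per arm.
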